4.6. Efficacy Evaluation

Following the early termination of the study and due to the number of subjects randomized being substantially lower than the target number if the study had been fully enrolled, no efficacy analyses are planned.

Efficacy data from eDiaries, eCRF, quality of life questionnaires and other ePROs questionnaires will be reported in listings.

Sponsor:	ObsEva		
Protocol:	18-OBE2109-002		
Document Version No.:	1.0	Document Date:	18-MAY-2021

4.7. Pharmacokinetic Evaluations

Following the early termination of the study and due to the number of subjects randomized being substantially lower than the target number if the study had been fully enrolled, no pharmacokinetic analysis is planned.

Pharmacokinetic data will be reported in a listing.

4.8. Safety Analyses

Safety analyses will be conducted using the Safety Population.

4.8.1. Extent of treatment exposure and compliance

4.8.1.1. Extent of treatment exposure

Duration of treatment (weeks) will be summarized for each treatment group. Duration is defined as: [(date of last treatment administration as described in section 4.2.12) - (date of first administration as collected in eCRF) +1] / 7.

Time on study (weeks) will be summarized for each treatment group, defined as: [(end of study date as described in section 4.2.12) – (first dose date) +1]/7

Exposure data will be reported in listings.

4.8.1.2. Compliance

Lingazolix/Placebo Grey blister (200 mg or matching placebo), Lingazolix/Placebo Pink blister (75 mg or matching placebo) and Add-back therapy compliance from the study treatment accountability page among the Day 1- End of main study treatment period will be summarized by treatment group.

If Lingazolix/Placebo and Add-back therapy compliances from accountability data are missing, compliance will be computed from daily diary data.

Compliance will be computed as the number of days with pink tablet/grey tablet/Add-back capsule taken *100 divided by the number of days in the period (Month 6 visit date/withdrawal date - Day 1). Data from “Today” will be used primarily. If data from today is missing, date from “Yesterday” will be considered. If the e-diary is not completed for a day (neither “Today” nor “Yesterday”), it will be assumed that no intake of drug was taken on that day.

Study treatment overdose and misuse will be reported in a listing.

Compliances will be reported in a listing.

Sponsor:	ObsEva		
Protocol:	18-OBE2109-002		
Document Version No.:	1.0	Document Date:	18-MAY-2021

4.8.2. **Adverse Events**

Adverse events will be coded using the Medical Dictionary for Regulatory Activities (MedDRA) and displayed in tables and listings using System/Organ/Class (SOC) and Preferred Term.

Analyses of adverse events will be performed for those events that are considered treatment emergent (TEAEs), where treatment emergent is defined as AEs with a start date on or after the first dose of study drug through 30 days after discontinuation of study drug or Month 6 visit date, or any event that was present at baseline but worsened in intensity or was subsequently considered drug-related by the investigator through the end of the study.

Adverse Event tables will be presented for the following periods: Day 1 to Month 6 (treatment period) and Month 6 to Month 6 FU (follow-up period) as defined in section 4.2.12.

Adverse events starting more than 30 days after end of treatment will be considered as post-treatment AE.

Note: if an adverse event started after or at Month 6 visit date and if the subject entered the extension period, this adverse event will not be displayed for the main study, but only for the extension study.

For each of these 2 study periods, an overall summary table will be prepared presenting, by treatment group and overall, the number and percentage of subjects with

- any AE,
- any TEAE,
- any post-treatment AE (displayed only for the follow-up period)
- Severe TEAE,
- any TEAE assessed by the Investigator as related to Linzagolix,
- any TEAE assessed by the Investigator as related to add-back therapy,
- any TEAE leading to permanent discontinuation of IMP,
- any serious adverse event,
- any serious Treatment Emergent Adverse Event,
- any serious Treatment Emergent adverse event related to Linzagolix,
- any serious Treatment Emergent adverse event related to add-back therapy,
- Any TEAE leading to permanent discontinuation of IMP
- any fatal TEAE (where outcome is “Fatal”)

In these tabulations, each subject will contribute only once (i.e., via the most related occurrence or the most intense occurrence) to each of the incidence rates in the descriptive analysis, regardless of the number of episodes experienced.

Sponsor:	ObsEva		
Protocol:	18-OBE2109-002		
Document Version No.:	1.0	Document Date:	18-MAY-2021

Adverse events are summarized by subject incidence rates, therefore, in any tabulation, a subject contributes only once to the count for a given adverse event (SOC or preferred term).

The number and percentage of subjects with any treatment-emergent adverse event, with any treatment-emergent adverse events assessed by the Investigator as related to treatment (definite, probable, or possible relationship), with any serious treatment-emergent adverse event, with any non-serious treatment-emergent adverse event, with treatment-emergent adverse event leading to permanent discontinuation of IMP and with fatal treatment-emergent adverse event will be summarized by treatment group and overall. Tabulation by severity will also be made. In these tabulations, each subject will contribute only once (i.e., the most related occurrence or the most intense occurrence) to each of the incidence rates in the descriptive analysis, regardless of the number of episodes.

The ongoing status of each Adverse Event will be derived based on Adverse Event Outcome as the following:

AE Outcome	AE Ongoing Status
Fatal	No
Not recovered/not resolved	Yes
Recovering/resolving	Yes
Recovered/resolved	No
Recovered/resolved with sequelae	No
Unknown	Unknown
Missing	Missing

The ongoing status collected in eCRF will be ignored.

The number and percentage of subjects with any post-treatment adverse event will be summarized on the follow-up period by treatment group and overall.

The number of events will be also displayed for summary of AEs, for analysis of TEAE, serious TEAE non-serious TEAE and for post-treatment AE, by SOC and PT.

No formal hypothesis-testing analysis of adverse events incidence rates will be performed.

All adverse events occurring on study will be listed in subject data listings.

By-subject listings also will be provided for the following: Treatment Emergent Adverse event, serious Treatment Emergent adverse events; Treatment Emergent adverse events leading to permanent discontinuation of IMP and leading to permanent discontinuation of IMP leading to death; post-treatment adverse event.

Sponsor:	ObsEva		
Protocol:	18-OBE2109-002		
Document Version No.:	1.0	Document Date:	18-MAY-2021

4.8.3. **Bone Mineral Density (BMD) by DXA**

BMD of femoral neck, total hip and lumbar spine will be assessed by DXA at Baseline, Month 6 and Month 6 follow-up. Unacceptable DXA assessments (accepted="No") will not be summarized (hip, spine and femur considered separately).

In case of repeated values due to BMD loss $\geq 5\%$, the initial scan will be used in summaries. Initial and repeated scan values will be reported in the listings.

Calibrated values will be used if available, otherwise initial values will be considered.

BMD, expressed as both absolute values and Z-scores will be summarized at each visit in terms of actual values, changes from baseline for each anatomic location. For absolute values only, percent change from baseline and 95% confidence interval for the mean percent change from baseline within each group will be produced at each time point.

Percent change from baseline to Month 6 and Month 6 follow-up will be described and will also be summarized in categories of percentage with the following classes:

- No change or increase,
- Decrease $\leq 3\%$,
- Decrease $> 3\% \text{ and } \leq 5\%$,
- Decrease $> 5\% \text{ and } \leq 7\%$,
- Decrease $> 7\% \text{ and } \leq 8\%$,
- Decrease $> 8\%$.

All data will be listed.

4.8.4. **Laboratory Data**

Clinical laboratory values will be expressed using conventional SI units.

Hematology, coagulation parameters, chemistry and lipids were assessed at screening and at each visit during the treatment period, as well as at the M1 FU and M3 FU visits. E2, progesterone (P4) and LH are assessed at each visit during the treatment period (not at screening visit), as well as at the M1 FU and M3 FU visits. Serum levels of the anti-Müllerian hormone (AMH) and fasting glucose were assessed on Day 1 only. Serum levels of the sex hormone-binding globulin (SHBG) were assessed on Day 1 and Month 3 and Month 6 visits.

Blood samples were to be analyzed by the central laboratory.

For hematology, coagulation parameters, chemistry and lipids, the actual value and change from baseline will be summarized for each visit for each treatment group. In the event of repeated values, the last non-missing value per study day/time will be used.

Evaluation of shifts for changes from baseline to all visits, and to last on-treatment value (including unscheduled assessments) according to the normal ranges with categories "Low", "Normal", "High"

Sponsor:	ObsEva		
Protocol:	18-OBE2109-002		
Document Version No.:	1.0	Document Date:	18-MAY-2021

and according to normal/abnormal/abnormal clinically significant information collected otherwise, will be provided. Note that a value will be considered as “on-treatment” if the collection is performed between the first and last intake administration (included).

For Liver Function Test (LFT) parameters (ALT, AST, ALP, total bilirubin, direct bilirubin, indirect bilirubin, GGT, albumin, LDH and Creatine Kinase), evaluation of shifts for changes from baseline will be extended by the worst (highest) on-treatment value (including unscheduled assessments) according to the normal ranges with categories “Low”, “Normal”, “High” will be provided.

For the lipid panel (Triglycerides, HDL, LDL, Total Cholesterol, LDL/HDL ratio), the percent change from baseline to each on-study visit will also be summarized.

For serum levels of P4, SHBG and LH, only the actual values at each time point will be summarized. Note: in the event of repeated values, the last non-missing value per study day/time will be used.

In addition, for E2, the proportion of subjects with the following categories:

- E2 <20 pg/mL,
- E2 between ≥20 and <60 pg/mL,
- E2 ≥60 pg/mL

at each visit and for each treatment group will be provided in tables.

For P4, since P4 above 10 nMol/L may suggest luteal activity and hence ovulation, the proportion of subjects with P4 >10.0 nMol/L at least once from Study Day 1 to Month 6 will also be provided in tables.

The number and percentage of subjects with cholesterol values in the following categories

- LDL ≥ 160 mg/dL
- LDL ≥ 190 mg/dL
- HDL < 40 mg/dL

will be reported at each visit.

Shift tables from baseline to each visit will be provided for the following LDL and Triglycerides categories (after rounding to integer values if necessary).

LDL:

- 0: ≤ 130 mg/dL
- 1: 131 to 159 mg/dL
- 2: 160 to 189 mg/dL
- 3: ≥ 190 mg/dL

Triglycerides:

Sponsor:	ObsEva		
Protocol:	18-OBE2109-002		
Document Version No.:	1.0	Document Date:	18-MAY-2021

- 0: ≤ 150 mg/dL
- 1: 151 to 300 mg/dL
- 2: 301 to 500 mg/dL
- 3: 501 to 1000 mg/dL
- 4: >1000 mg/dL

All laboratory data will be provided in data listings. Serum levels of the anti-müllerian hormone (AMH) and fasting glucose only recorded at Day 1 will be included in the listings.

A subset listing will be presented for all abnormal clinically significant laboratory values.

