## 10.2 OUTLINE OF STUDY PROCEDURES AND ASSESSMENTS

All post-baseline visits should take place at the end of the defined period (i.e. Month 1 visit should be scheduled at the end of Month 1, Month 2 visit should be scheduled at the end of Month 2, etc.). One month is defined as 28 days/4 weeks. Post-baseline visit dates are calculated from Day 1 visit date :

- Month 1 (Day 29), Month 2 (Day 57), Month 3 (Day 85), Month 4 (Day 113), Month 5 (Day 141) and Month 6 (Day 169) for the Treatment Period,
- Month 1 FU (Day 197), Month 2 FU (Day 225), Month 3 FU (Day 253), Month 4 FU (Day 281), Month 5 FU (Day 309) and Month 6 FU (Day 337) for the Follow-up Period.

A window of  $\pm$  3 days is allowed for each visit scheduled during the treatment period. A window of  $\pm$  7 days/1 week is allowed for each visit scheduled during the follow-up period. The visit schedule is illustrated in Figure 2 below:

\* Subjects who discontinue treatment prior to Month 3 will not enter the follow-up period.

\*\* At the end of the 6-month follow-up, subjects with a BMD decrease from baseline of > 1.5% for lumbar spine and/or > 2.5% for total hip will have an additional DXA scan 6 months later.

Figure 2 : Schedule of Visits

The timing of events is shown in the Schedule of Assessments (Appendix A and Appendix B).

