#### Withdrawal during treatment period:

Subjects who discontinue between Day 1 and Month 3 should undergo the procedures required at Month 6 (except the DXA scan and the endometrial biopsy if a biopsy was obtained at screening) and will not enter the 6-month follow-up period.

Subjects discontinuing the study treatment between Month 3 and Month 6 should undergo the procedures required at Month 6. These subjects will enter a 6-month follow-up period and will continue daily eDiary recording for 6 months and up to Month 6 FU visit in order to continue to collect efficacy data.

PK sampling is not required if the subject had no IMP administration the day prior to the withdrawal visit.

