## 11.2 DOSAGE AND ADMINISTRATION

Linzagolix and corresponding placebo treatments will be supplied as film-coated tablets for oral administration and given as monthly treatment kits (Figure 5).

ABT and corresponding placebo will be supplied as red capsules and given as 3-monthly treatment kits.

IMP treatment will start on Day 1 and will be administered once daily up to the day preceding the Month 6 visit. The subjects will have to swallow two tablets of linzagolix/placebo and one capsule of ABT/placebo, ideally at the same time each day.

On the day of a study visit, the subject must take the study medication at site, after the PK blood sample collection, except on Day 1 visit where the study medication must be taken before the PK blood sample collection (at least 1.5 h before). The site staff will record in the eCRF the time of study medication intake. The linzagolix/placebo tablets must be taken from the kits dispensed on that visit (and not from the previously dispensed kits). On Day 1 and Month 3 visits, ABT/placebo capsules must be taken from the kits dispensed during these visits. On Month 1, 2, 4 and 5 visits, ABT/placebo capsules must be taken from the previously dispensed kits.

The treatment groups are described below:

Treatment group	Daily dose Day 1 to Month 6			
	Linzagolix active tablets	Linzagolix placebo tablets	ABT active capsules	ABT placebo capsules
75 mg	1 × 75 mg	1 × placebo 200 mg	None	1 capsule
200 mg	1 × 200 mg	1 × placebo 75 mg	1 capsule	None
Placebo	None	1 × placebo 75 mg AND 1 × placebo 200 mg	None	1 capsule

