4.2.12. Last treatment administration date, End of Study date and Period definitions

The last treatment administration date will be defined as the date of treatment termination recorded in the main period eCRF page. If this date is missing, the last date with a drug intake in eDiary prior to the Month 6 date or, for subjects who discontinued, the last date with available drug intake information in the subject eDiary will be used.

The end of study date will be the last assessment date in the main study defined as last eCRF or ediary date prior to and not including Month 6 for subjects who entered the Extension, and the last eCRF or ediary date in the main study or main follow-up if not. This will not necessarily be the same date as last assessment date as recorded in the eCRF.

Note: For summaries by visit (efficacy or safety), the Month 6 assessments will be included in the main study analyses. For Adverse Events, Concomitant Medications and Daily diaries, data collected on Month 6 date will be part of the extension for subjects entering the extension study and be part of the Follow-up period for subjects entering the main study follow-up period.

The main treatment period will be defined as Day 1 up to (Month 6 date -1) or the treatment discontinuation date.

The main follow-up period will be defined as the Month 6 date or (treatment discontinuation date+1) up to the end of study date (for subjects who entered into the main follow-up period).

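### The diary-based compliance denominator in SAP 4.8.1.2 is right for completers but miscounts treatment days for women who stop early

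*SAP*

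**What the plan says.** SAP 4.8.1.2 makes the accountability page the main source: "compliance from the study treatment accountability page among the Day 1- End of main study treatment period will be summarized by treatment group". The diary is a fallback. If the "compliances from accountability data are missing, compliance will be computed from daily diary data", as the number of days with the tablet or capsule taken, times 100, "divided by the number of days in the period (Month 6 visit date/withdrawal date - Day 1". The SAP does not define the withdrawal date. Its section 4.2.7 speaks of withdrawal both in the treatment period and in follow-up.

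Two other sections count the same days differently. For exposure, SAP 4.8.1.1 starts from the last treatment administration date and subtracts the "date of first administration as collected in eCRF) +1] / 7", so both end days are counted. SAP 4.2.12 states: "The main treatment period will be defined as Day 1 up to (Month 6 date -1) or the treatment discontinuation date". For a woman who stops early, the period therefore runs through the day she discontinues treatment.

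The protocol fixes the completer's calendar. Under section 11.2, "IMP treatment will start on Day 1 and will be administered once daily up to the day preceding the Month 6 visit", and section 10.2 places "Month 5 (Day 141) and Month 6 (Day 169) for the Treatment Period". Of women who stop treatment between Month 3 and Month 6, Protocol 10.7.2 says: "These subjects will enter a 6-month follow-up period".

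**The concern.** One subtraction serves two kinds of end date. The Month 6 visit is the day after the last dose, so subtracting Day 1 from it gives exactly the number of dosing days. A withdrawal date has no fixed relation to the last dose. It may be the last dose day, in which case the denominator is one day short, or a later visit, in which case it includes days on which no drug was due.

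At stake is the compliance column of Table 14.1.11.1 and the entries in Listing 16.2.5.3. After early termination the SAP reports safety only, for all subjects whatever their treatment duration, and a reader uses compliance to judge how much of the assigned drug those data reflect. In early stoppers on the diary fallback, the percentage would mix adherence with the timing of the exit visit. It would also sit beside a treatment duration counted on a different basis in the same table.

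**Working it through.** The documents state no compliance figure, so there is none to reproduce. The check is to apply the formula to women who missed no dose, for whom the answer should be 100%.

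**Inputs.** One dose per day from Day 1 (Protocol 11.2); Month 6 visit nominally on Day 169 (Protocol 10.2); numerator and denominator as in SAP 4.8.1.2. Let d be the study day of the last dose and L the number of days from the last dose to the withdrawal date. The documents give no values of L, so those below are assumptions.

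**Completer.** Doses fall on Days 1 to 168 and the denominator is 169 − 1 = 168, so compliance is 100 × 168/168 = 100%. The result is the same at the edges of the ±3-day window (165/165 for a Day 166 visit, 171/171 for Day 172). The formula is right here.

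**Early stopper, general form.** Doses taken = d; denominator = (d + L) − 1; compliance = 100 × d/(d + L − 1).

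**Withdrawal date equal to the last dose day (L = 0).** This is what results if the withdrawal date is read as the treatment discontinuation date that closes the period in 4.2.12, and a dose was taken that day. Compliance is 100 × d/(d − 1):

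- d = 7: 7/6 = 116.7%
- d = 28: 28/27 = 103.7%
- d = 84: 84/83 = 101.2%
- d = 112: 112/111 = 100.9%
- d = 1: denominator zero. The Safety Analysis Set requires only one dose (SAP 3.1), and Protocol 10.7.2.1 has discontinuation rules tied to Day 1 results, so very early stops are foreseen.

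**Withdrawal date after the last dose.** L = 1 gives exactly 100%. Beyond that the result falls below 100%:

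| Last dose | L = 7 | L = 14 | L = 28 |
|---|---|---|---|
| Day 28 | 28/34 = 82.4% | 28/41 = 68.3% | 28/55 = 50.9% |
| Day 84 | 84/90 = 93.3% | 84/97 = 86.6% | 84/111 = 75.7% |

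The plan foresees such gaps, though not their length: Protocol 10.7.2 and SAP 4.2.7 both waive PK sampling when no dose was taken on the day before the withdrawal visit.

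**With the 4.8.1.1 count.** The denominator is last dose − first dose + 1 = d, so a fully adherent stopper has 100 × d/d = 100% at any stopping day (28/28, 84/84, 112/112).

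**The case against.** The case for leaving this alone has four parts.

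- **It is a fallback.** Accountability is scheduled at every visit from Month 1 to Month 6 (Protocol Appendix A), and early stoppers undergo the Month 6 procedures, which include final accountability. The diary formula applies only where those data are missing. This stands. Missing accountability is plausible, since Protocol 5.7 describes telephone calls replacing site visits during the pandemic, but the documents give no share.
- **Little depends on it.** Efficacy analyses are dropped, the SAP has no per-protocol set or compliance cut-off, and actual treatment in SAP 3.1 is assigned from diary day counts rather than from this percentage. Treatment duration is reported with a consistent formula in the same table. This stands too.
- **Under the 4.2.12 reading it is only an off-by-one.** For stops at Day 28 or later the excess is under 4 points. That is correct, but a percentage above 100 or a zero denominator is still a wrong output from a stated rule.
- **Counting to withdrawal is defensible.** It captures a woman who silently stops her tablets before formally leaving. This has some force. It argues for defining the date, and it is a real cost of the change proposed below.

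A reader might infer something stronger: that women who stop between Month 3 and Month 6 will show compliance near 40%, because they remain in the study for up to 168 drug-free days. Taking study exit as the withdrawal date does give, for a Day 112 stop, 112/(112 + 168 − 1) = 40.1%. The documents do not support that reading. Section 4.8.1.2 confines compliance to the main study treatment period, 4.2.12 ends that period at treatment discontinuation, and the table title stops at Month 6. Without the study-exit reading, a figure that low needs an assumed gap: 43 days for a Day 28 stop, 127 days for a Day 84 stop.

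**Conclusion.** The point holds as a local error in a stated rule. The denominator is correct for completers. For early stoppers it disagrees with the SAP's own treatment period and its own exposure count, and it depends on a date the SAP does not define.

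For a fully adherent woman the error is upward if the withdrawal date is the last dose day: large only for very early stops, and about 1 to 4 points from Day 28 on. It is downward if the withdrawal visit comes more than one day later, by an amount set entirely by the gap. The downward figures rest on assumed gaps and illustrate the mechanism; they are not estimates for this trial.

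The consequence is descriptive only, in one table and one listing. The number of women affected cannot be derived, because neither the share with missing accountability data nor the number of early stoppers is given. A reader might also infer a bias between arms. That would require stopping, or the timing of exit visits, to differ by arm, and nothing in the documents shows it.

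**What to change.** In SAP 4.8.1.2, keep Month 6 visit date − Day 1 for completers. For women who stop early, replace the denominator with last treatment administration date (per 4.2.12) − first dose date + 1. State that this date is the treatment discontinuation date that closes the main treatment period, so that the denominator equals the period in 4.2.12 and agrees with the exposure count in 4.8.1.1. Completers stay at 168/168, and a Day 1 stop has a denominator of 1.

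The completer formula should not be replaced by the last-dose count: a completer who stopped taking tablets before Month 6 without a recorded discontinuation should still have those days counted as missed.

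The cost is one line of SAP text and one line of code. The downside is that, for early stoppers, days between the last recorded treatment date and formal withdrawal no longer count as non-adherence. A footnote to Table 14.1.11.1 should say so.
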